To monitor for development of intense impulsive behavior, the Minnesota Impulsive Disorders Interview (MIDI)⁴⁶ will be administered at the times indicated in [Table 3](#) or whenever relevant symptoms emerge. The entire interview is to be completed at V1. If the subject's impulsivity during the Screening Period is judged to be clinically significant in the judgment of the Investigator, they will be excluded from participation in the study and referred for appropriate follow-up care. Any subject noted to have intense impulsive behavior during the study as assessed by the MIDI, or via clinical interview, will be evaluated immediately by the Investigator. The study designated physician should also be notified. The MIDI will be administered as indicated in [Table 3](#).

Columbia-Suicide Severity Rating Scale (C-SSRS)

The Columbia-Suicide Severity Rating Scale (C-SSRS)⁴⁷ is a systematically administered instrument designed to assess suicidal behavior and ideation, track and assess all suicidal events, as well as the lethality of attempts. Additional features assessed include frequency, duration, controllability, reason for ideation, and deterrents. The C-SSRS is considered a low-burden instrument as it takes less than 5 minutes to administer.

Any subject noted to have suicidal ideation with plan within the last year, either via answering "yes" to question 4 and/or question 5 to the suicidal ideation portion of the C-SSRS, or via clinical interview, will be evaluated immediately by the Investigator. The study designated physician will also be notified. In addition, if the subject expresses suicidal ideation at any time during the study, the Investigator should be immediately notified as well as the study designated physician.

Under no circumstances should a subject who has positively endorsed or expressed suicidal ideation be left alone, be allowed to exit the site, or go home before a qualified medical professional has evaluated the subject's risk.

The "Already Enrolled Subjects" C-SSRS will be the first assessment scale administered to the subject. At each subsequent visit, the "Since Last Visit" C-SSRS scale should be administered.

The C-SSRS will be administered at the times outlined in [Table 3](#).

Non-Motor Symptom Scale (NMSS)

Non-motor symptoms associated with Parkinson's disease can result in substantial patient burden. The NMSS is a comprehensive validated tool measuring a broad range of non-motor symptoms in PD patients. The scale is aimed to be practical and quantitative, encompassing the whole range of non-motor symptoms experienced by people with PD. The NMSS measures the frequency and severity of these symptoms and is comprised of 30 questions that cover 9 domains of patient symptom experience (cardiovascular/falls,

sleep/fatigue, mood/cognition, perceptual problems/hallucinations, attention/memory, GI tract, urinary, sexual function, and miscellaneous [pain, taste/smell, weight change, excessive sweating]).^{48,49} The NMSS measures the burden of non-motor symptoms by weighting each symptom by its frequency and severity; thereby, providing a quantitative measure that captures infrequent but severe symptoms (e.g., hallucinations) and less serious but frequent symptoms (e.g., fatigue, constipation) and provides the overall global burden for patients. Scores are calculated for each domain as well as a total score. Severity and frequency are rated using a 4-point scale ranging from 0 (none) to 3 (severe; major source of distress or disturbance to subject) for severity and from 1 (rarely) to 4 (very frequent [daily or all the time]) for frequency. The total NMSS score ranges from 0 to 360. A negative change from Baseline to end of Maintenance indicates an improvement in NMSS. It is required that only trained and certified health professionals will administer the scale. For this study the NMSS will be performed by an approved, trained, blinded, central rater, who should be a specialist on movement disorders with previous experience using the NMSS scale in advanced PD patients. To be qualified by the Sponsor and the rater vendor, all raters must have participated in the Rater Training and have a current valid Rater Certificate. The qualified rater will complete the NMSS at the times indicated in [Table 3](#).

PDSS-2

Although a number of scales exist in evaluating sleep disturbances, only 3 are endorsed and recommended by the Movement Disorders Society.⁵⁰ One such scale specific for Parkinson's disease is the Parkinson's Disease Sleep Scale (PDSS), which has been modified to the PDSS-2. The purpose of the PDSS-2 scale is to characterize the various aspects of nocturnal sleep problems in PD patients. The PDSS-2 instrument has been shown to be reliable, valid, precise, and a potentially treatment responsive tool for measuring nocturnal disabilities and sleep disorders in PD.⁵¹ PDSS-2 consists of 15 questions evaluating motor and NMS at night and upon waking, as well as disturbed sleep grouped into 3 domains: motor symptoms at night (5 items), PD symptoms at night (5 items), and disturbed sleep (5 items). Specifically, questions assess overall sleep

quality, insomnia, sleep fragmentation, RLS and PLMS, RBD, hallucinations, nocturia, nocturnal immobility, pain and cramps, morning akinesia, cramps and tremor, and sleep apnea. The PDSS-2 was developed from the PDSS based upon the need for a treatment-measuring tool containing PD-specific sleep disorders. The instrument was extended to address specific sleep disturbances such as RLS, akinesia, pain, and sleep apnea. Daytime sleepiness was removed from the PDSS-2, as it is a more complex PD symptom. To increase ease of use, the visual analogue scale of the PDSS was transformed into a frequency measure in the PDSS-2. The frequency is assessed for the 15 sleep problems based on a 5-point Likert-type scale (ranging from 0 [never] to 4 [very often]). Scores are calculated for each domain as well as a total score. The recall period is for the past week. For this study the PDSS-2 will be performed by an approved, trained, blinded central rater, who should be specialist on movement disorders with previous experience using the NMSS scale in advanced PD patients. To be qualified by the Sponsor and the rater vendor, all raters must have participated in the Rater Training and have a current valid Rater Certificate. The qualified rater will complete the PDSS-2 at the times indicated in [Table 3](#).

The PDSS-2 will be completed at the times indicated in [Table 3](#).

Unified Parkinson's Disease Rating Scale (UPDRS)

The Unified Parkinson's Disease Rating Scale (UPDRS)⁵² is an Investigator-used rating tool to follow the longitudinal course of Parkinson's disease. Every effort should be made by the Investigative sites to ensure that each subject is rated by the same rater throughout the subject's participation in the study. The UPDRS assessment will be performed by an approved, trained rater. To be qualified by the Sponsor and the rater vendor, all raters must have participated in the Rater Training and have a current valid Rater Certificate.

The UPDRS is made up of the following sections:

- Part I – Mentation, Behavior, and Mood
- Part II – Activities of Daily Living

- Part III – Motor Examination
- Part IV – Complications of Therapy (including dyskinesias)
- Part V – Modified Hoehn and Yahr Staging

Some sections require multiple grades assigned to each extremity. UPDRS total score ranges from 0 to 176, with 176 representing the worst (total) disability, and 0 no disability. Additionally, Questions 32, 33, and 34 of the UPDRS will be totaled to evaluate dyskinesias.

During Visit 1 the UPDRS Part III will be done during practically defined "Off" time and best "On" time. The practically defined "Off" time UPDRS will be done in the morning prior to the subject taking their first daily dose of anti-PD medication. The best "On" time rating should be done approximately 1 to 2 hours post any morning dose of study drug or PD medications but prior to lunch. If possible, the UPDRS should be done at the same time of day throughout the trial. The "Off" time UPDRS will only be done during Screening; at all other times a complete UPDRS (Parts 1 through 5) will be done during "On" time.

The UPDRS will be obtained at the times indicated in [Table 3](#).

Health Outcome Measurements

Clinical Global Impression of Change (CGI-C)

The CGI-C is a clinician's rating scale for assessing Global Improvement or Change. The CGI-C rates improvement by 7 categories: very much improved, much improved, minimally improved, no change, minimally worse, much worse, very much worse. Proportion of responders who had at least "minimally improved" in CGI-C ratings will be assessed.

A qualified rater will administer the CGI-C to the subject at the times indicated in [Table 3](#).

Patients' Global Impression of Change (PGIC)

The PGIC⁵³ is a 7-point response scale. The subject will be asked by the Investigator or qualified designee to rate their change in status using the following 7-point scale:

1 = Very much improved, 2 = Much improved, 3 = Minimally improved, 4 = No change, 5 = Minimally worse, 6 = Much worse, 7 = Very much worse.

The responses of "Very much improved," "Much improved" and "Minimally improved" on the PGIC will be used to define responders. A qualified rater will administer the PGIC to the subject at the times indicated in [Table 3](#).

Parkinson's Disease Questionnaire (PDQ-8)

The PDQ-8⁵⁴ is a disease-specific instrument designed to measure aspects of health that are relevant to subjects with PD, and which may not be included in general health status questionnaires. The PDQ-8 is a self-administered questionnaire. Each item is scored on the following 5-point scale: 0 = Never, 1 = Occasionally, 2 = Sometimes, 3 = Often, 4 = Always (or cannot do at all, if applicable).

Higher scores are consistently associated with the more severe symptoms of the disease such as tremors and stiffness. The results are presented as eight discrete domain scores and as a summary index. The PDQ-8 domain scores and summary index range from 0 to 100, where lower scores indicate a better perceived health status.

A qualified rater will administer the PDQ-8 to the subject at the times indicated in [Table 3](#).

Parkinson Anxiety Scale (PAS)

The Parkinson Anxiety Scale (PAS) is a new scale developed specifically to measure severity in anxiety in Parkinson's disease. Lack of adequate validation data in the existing anxiety scales led to the development of the PAS. The PAS is a brief scale designed to measure anxiety in PD, rated by patients or clinicians. It contains three dimensions: persistent anxiety, episodic anxiety, and avoidance behavior. It is an easy and brief to

administer, and has better clinimetric properties than existing anxiety rating scales.⁵⁵ Additionally a recent study has found that the PAS modified dimensions A and B provide valid and reliable measures of anxiety in PD that are comparable across raters.⁵⁶ A qualified rater will administer the PAS to the subject at Visits 3, 6, 7 and 8.

Geriatric Depression Scale (GDS-15)

The Geriatric Depression Scale (GDS) is a short, self-report reliable and valid screening instrument for depression in the elderly. The response items are in a "Yes/No" format. The GDS was originally developed as a 30-item instrument but it was time-consuming and difficult for some patients to complete hence a 15-item version of the GDS was developed. The shortened form consists of 15 items chosen from the Geriatric Depression Scale-Long Form (GDS-L). These 15 items were chosen because of their high correlation with depressive symptoms in previous validation studies.⁵⁷ The GDS-15 has adequate discriminant validity for the diagnosis of major and minor depressive disorder.⁵⁸ Of the 15 items, 10 indicate the presence of depression when answered positively while the other 5 are indicative of depression when answered negatively. The GDS items focus on the psychological aspects of depression, thus avoiding symptom overlap with other disorders or aging in general. The GDS-15 can be completed in approximately 5 to 7 minutes, making it ideal for patients who are easily fatigued or are limited in their ability to concentrate for longer periods of time. A qualified rater will administer the GDS-15 to the subject to assess depression at Visits 3, 6, 7 and 8.

King's PD Pain Scale

The King's PD Pain Scale is an easy to administer novel clinical PD specific pain scale developed with a focus on sub classification of nociceptive and neuropathic pain. It was specifically developed to assess pain among Parkinson's disease patients since no validated PD specific scales existed to characterize the various types of pain in PD. The scale consists of seven domains of pain including musculoskeletal, chronic, fluctuation related, nocturnal, oro-facial, local limb pain/edema/swelling and radicular pain. The scale measures the frequency and severity of these symptoms. The clinimetric properties

of this instrument have been recently evaluated.⁵⁹ A qualified rater will administer the King's PD Pain Scale to the subject to assess for PD specific pain at Visits 3, 6, 7 and 8.⁵⁹

Titration Visits (LCIG Group Only)

Dose Titration Diary and LCIG Prescription Record (LCIG Group Only)

While the subject is in the hospital, the study staff may use the Dose Titration Diary as a tool to achieve dose optimization. In the event it is used it should be completed hourly until the dose is optimized and then once AM and once PM it will be completed until the subject is discharged. All adjustments can be recorded on the Dose Titration Diary allowing the Investigator to appropriately adjust, if needed, the following day's morning dose, continuous infusion rate and extra dose until the subject is optimized.

The subject's pump settings for the first infusion of LCIG, the pump settings at the conclusion of each calendar day are to be recorded on the appropriate eCRF.

Following the initial titration period, the site should record the subject's pump settings (morning dose in mL, continuous infusion rate in mL/hr, and lock level) at the conclusion of each clinic visit on the study drug prescription record.

Subject Dosing Diary (LCIG and OMT Groups)

The subject dosing diary should be completed during the 72-hour period (3 days) prior to each clinic visit, as indicated in [Table 3](#). Subjects should be reminded with a phone call prior to each visit to complete the Subject Dosing Diaries and to reinforce the importance of Subject Dosing Diary completion.

Subjects in the LCIG group will record the date and actual clock time of the LCIG pump start and pump stop as well as LCIG extra doses in the diary. In addition, the subject will be instructed to record all oral levodopa-carbidopa taken on the Subject Dosing Diary days.

Subjects in the OMT group will record all anti-parkinsonian medications taken on the Subject Dosing Diary days in the diary.

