- If the larger of the 2 P values is > 0.05 , then compare the smaller P value with 0.025. The second endpoint is statistically significant if the P value is ≤ 0.025 ; otherwise, neither endpoint is considered statistically significant.

Secondary Efficacy Analyses

There are 3 key secondary endpoints:

- PDQ-8 summary index
- CGI-C
- UPDRS Part II score

The key secondary efficacy endpoints will be analyzed with the same MMRM model as the primary efficacy variables. For CGI-C, the scores collected at the visits will be the dependent variable.

If both primary efficacy variables are statistically significant after adjusting for multiplicity, the Stepwise Gatekeeping Procedure will be utilized and the 3 key secondary endpoints will be tested using the Hochberg procedure with significance level of 0.05.

Other secondary endpoints below will be analyzed with the same MMRM model as the primary efficacy variables:

- NMSS domain scores
- PDSS-2 domain scores
- UPDRS total score, Part I score, Part III score, Part IV score
- PGIC
- Parkinson Anxiety Scale (PAS) total and subscale scores
- Geriatric Depression Scale (GDS-15) score

For the analysis on PGIC, the scores collected at the visits will be the dependent variable.

Statistical Methods (Continued):

Safety:

Safety Dataset and Treatment Period

All safety analyses will be performed on the safety dataset which will include all subjects who are randomized to the optimized medical treatment, and all subjects who are randomized to LCIG and received at least one dose of study drug. The treatment period for safety is the same as what is defined for efficacy.

Safety Analyses

Safety analyses will include summaries of adverse events, device-related product complaints, vital signs and special labs.

Determination of Sample Size

Approximately 88 subjects will be enrolled into the study and randomized in a 1:1 ratio to either OMT or LCIG. There are no results on NMSS or PDSS-2 available from randomized trials comparing LCIG and OMT. Interim data from ongoing Phase 3b Study M12-920 showed that the improvement in NMSS total score from baseline to Week 12 is 24.8 in the LCIG arm with standard deviation of 24. Results from Zibetti et al (2013) showed that the improvement in PDSS-2 total score after an average of 3.5 months of LCIG treatment was 13.1. The standard deviation was not provided and is estimated to be 12.2 assuming the correlation between baseline and follow-up visits is 0.5.

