A Neurological Examination focusing on symptoms and signs of polyneuropathy (light touch and pinprick sensation, vibratory sensation), deep tendon reflexes, and strength assessments will be performed at the times indicated in [Table 3](#). The Neurological Examination should be bilateral and be done during the subject's "On" time.

Any abnormalities or symptoms identified at Visits 1, 2 and 3 will not be recorded as adverse events but will be recorded in Medical History eCRF. Any new abnormalities or symptoms or symptoms that change in severity or frequency following randomization for the OMT group and the first dose of IP for the LCIG group will be recorded as adverse events.

The Neurological Examination will assess:

- Cranial nerves – assessment of cranial nerves II – XII
- Motor system – assessment of tone, strength and abnormal movements
- Sensory system – including light touch, pinprick, joint position and vibratory sense
- Reflexes – assessment of deep tendon reflexes and plantar responses (Babinski sign)
- Coordination – assessment of upper and lower extremities
- Gait – assessment of base and tandem gait

The Neurological Examination performed at Visit 1, will serve as baseline for clinical assessment.

Dermatological Assessment

A comprehensive assessment by an experienced dermatologist for the presence of any suspicious skin lesions and subsequent evaluation for melanoma will be performed prior to V2 and at Week 26/Premature Discontinuation. If a suspicious lesion is present, a biopsy should be obtained for proper diagnosis and confirmation that lesion does not meet exclusion criteria.

Positive screens will be exclusionary.

GI Examination

On or prior to V2, the Investigator and GI/surgeon will thoroughly evaluate the subject's risk of undergoing PEG-J procedure.

NJ and/or PEG-J Placement (LCIG Group Only)

For subjects randomized to LCIG, a temporary NJ tube may be used to optimize the dose of LCIG before treatment with a PEG-J is started. The NJ test phase should not last longer than 7 days. Following the NJ test phase, a PEG-J will be performed by a gastroenterologist proceduralist, or surgeon. Total time to titration via NJ and PEG-J should not exceed 14 days. Alternatively, subjects may proceed directly to placement of

PEG-J if deemed appropriate by investigator. Total time to titration via the NJ and PEG-J should not exceed 14 days. The number of days to titrate will vary for each subject.

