5.3.4 Safety Variables

Safety and tolerability over the course of the study will be assessed by the following measurements:

- Adverse event monitoring
- Neurological exams
- Clinical laboratory evaluations
- Electrocardiogram
- Vital signs and weight
- C-SSRS
- MIDI
- SAQ

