6.1.4 Adverse Event Collection Period

Protocol-related nonserious adverse events that occur after signing the informed consent, prior to the start of study drug administration, will be collected. All adverse events reported from the time of randomization until 30 days following last OMT dose, last study visit, discontinuation of study drug administration, removal of the PEG-J tube or Last LCIG Commercial Transition Visit have elapsed will be collected, whether solicited or spontaneously reported by the subject. In addition, serious adverse events and protocol related non serious adverse events will be collected from the time the subject signed the study-specific informed consent.

Adverse event information will be collected as shown in [Figure 3](#).

Figure 3. Adverse Event Collection

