8.1.4.6 Additional Safety Variables

The following additional summaries of safety measures will be prepared.

- The responses to the MIDI
- The responses to the C-SSRS
- The responses to the Sleep Attacks Questionnaire
- Percent of subjects who are cognitive impaired (MoCA score \leq 26)

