10.2.1 Adverse Event Overview

The number and percentage of subjects experiencing one or more adverse events in the following adverse event categories during the 26-week Treatment Period and during the Extension/Transition Period will be summarized.

- Any TEAE
- Any TEAE that was rated by the investigator as having a reasonable possibility of relationship to levodopa-carbidopa intestinal gel
- Any severe TEAE
- Any serious TEAE
- Any TEAE that led to discontinuation of study drug
- Any treatment emergent GI event (as defined in Section 10.2.3)
- Any TEAE other than a GI event (as defined in Section 10.2.3)
- A fatal TEAE
- All deaths

Serious adverse events with onset during the Screening Period for all subjects screened, adverse events and serious adverse events with onset after day of randomization and before day of initial device placement for the LCIG group, as well as adverse events during the transition period for LCIG subjects continuing LCIG commercial treatment will also be summarized.

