10.8 Analysis of Columbia-Suicide Severity Rating Scale (C-SSRS)

The Columbia-Suicide Severity Rating Scale (C-SSRS) is a systematically administered instrument developed to track suicidal adverse events across a treatment study. At Screening Visit 1 the C-SSRS will be administered to collect lifetime history as well as experience during the past year. At all other visits, the C-SSRS will collect experience since the last visit. Affirmative responses on the C-SSRS will be summarized for the following study periods and reporting timeframes: Screening: Lifetime and Past year; before randomization: Since last visit; and on or after Day 1: Since last visit.

Each summary will include the number and percentage of subjects in each treatment group with one or more affirmative responses to each of the 5 suicidal ideation questions,

each of the 6 suicidal behavior questions, any of the 5 suicidal ideation questions, any of the 6 suicidal behavior questions, any suicidal ideation or behavior question, and the non-suicidal self-injurious behavior question during the 26-week Treatment Period. No comparisons of treatment groups will be performed.

A summary of the number and percentage of subjects with one or more affirmative responses to the questions listed above during the Extension/Transition Period will also be provided for OMT/LCIG subjects who enter the Extension/Transition Period.

A listing will also be prepared that includes all subjects with 1 or more affirmative responses.

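### Protocol 5.3.1.1 keeps all Visit 1–3 neurological-examination findings out of adverse-event recording and starts LCIG recording at first dose, against 6.1.4; the examination also has no summary of its own in the SAP

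*Protocol*

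**What the plan says.** Protocol 5.3.1.1 describes a neurological examination aimed mainly at signs of polyneuropathy and gives two recording rules.

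- For the screening and randomization visits: "Any abnormalities or symptoms identified at Visits 1, 2 and 3 will not be recorded as adverse events". These findings go to the Medical History eCRF.
- For later visits, new abnormalities, or symptoms that have become more or less severe or frequent, "following randomization for the OMT group and the first dose of IP for the LCIG group will be recorded as adverse events".

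Protocol 6.1.4 sets the general collection period. All adverse events are collected from randomization in both arms, and "serious adverse events and protocol related non serious adverse events will be collected from the time the subject signed the study-specific informed consent".

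Protocol 8.1.4.2 and SAP 10.2.1 both plan to summarize "Serious adverse events with onset during the Screening Period for all subjects screened". Both also plan to summarize LCIG-group events that begin after the day of randomization and before initial device placement.

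"Neurological exams" is one of the safety variables in Protocol 5.3.4 and is repeated in SAP 4.6. The synopsis describes the safety analysis this way: "Safety analyses will include summaries of adverse events, device-related product complaints, vital signs and special labs". Protocol 8.1.4.6 adds MIDI, C-SSRS, sleep attacks and MoCA. None of these places mentions the neurological examination.

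**The concern.** A site that follows 5.3.1.1 literally would file every neurological finding from Visits 1 to 3 as history. That includes one that is serious or arose from a study procedure, which 6.1.4 asks the site to collect as an adverse event. The planned screening-period summary of serious events can only count what has been recorded as such.

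The start of recording in the LCIG group raises a similar problem. Between randomization and first dose, these subjects taper their other anti-Parkinson drugs and undergo tube placement. The paragraph gives no instruction for neurological findings in that interval, although 6.1.4 covers it and a summary is planned for part of it.

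Last, polyneuropathy is one of the three events of special interest in Protocol 6.1.1.3. The examination directed at its signs has no table or listing of results in either document.

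**Working it through.** No arithmetic beyond a count applies, so the check is a comparison of texts.

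**Step 1: recording rules by interval, LCIG group.** Randomization takes place at the end of Visit 3, so Visits 1 to 3 lie before it.

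| Interval | 5.3.1.1, neurological findings | 6.1.4 | Planned summary |
|---|---|---|---|
| Consent to randomization | Not adverse events; medical history | Serious and protocol-related events | Serious events with onset in screening |
| Randomization to device placement | No instruction | All adverse events | Separate LCIG summary (8.1.4.2, SAP 10.2.1) |
| Device placement to first infusion | No instruction | All adverse events | Inside the treatment-emergent period |
| From first infusion | New or changed findings are adverse events | All adverse events | Treatment-emergent and special-interest tables |

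The third row is the epoch that SAP 6.2 calls Device Before. It is empty when infusion starts on the day of placement.

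Row 1 contains a contradiction, but only for serious or protocol-related findings; 6.1.4 does not ask for other nonserious events before randomization. Rows 2 and 3 show a mismatch of start points. In the OMT group, 5.3.1.1 starts recording after randomization, which agrees with 6.1.4.

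The reach of rows 2 and 3 is limited. As far as Protocol Table 3 can be read, no neurological examination is scheduled at Visit 4, so these rows concern findings or symptoms noted outside a scheduled examination.

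**Step 2: the eight safety measures in SAP 4.6 against SAP section 10.**

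| Measure | SAP analysis |
|---|---|
| Adverse events | 10.2 |
| Neurological exams | none |
| Clinical laboratory | 10.3 |
| ECG | 10.5 |
| Vital signs and weight | 10.4 |
| C-SSRS | 10.8 |
| MIDI | 10.7 |
| Sleep attacks | 10.6 |

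Seven of eight have their own section, and 8 − 7 = 1 does not. Protocol 8.1.4.1 to 8.1.4.6 has no such analysis either.

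**Step 3: where the findings do go.** New or changed findings become adverse events and enter the tables of SAP 10.2.2. If their coded terms fall in the search, they also enter the polyneuropathy summaries (10.2.3) and listing (10.2.5). Findings from Visits 1 to 3 enter the medical history summary (SAP 7.3).

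**Step 4: baseline.** Protocol 5.3.1.1 names the Visit 1 examination as baseline. SAP 6.3 uses the last non-missing observation on or before randomization, which would normally be Visit 3. Any table of change needs one of these.

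**The case against.** The strongest reply is that 5.3.1.1 opens by leaving adverse-event collection to Section 6.0, and that 6.1.4 and the 24-hour rule for serious events in 6.1.1.2 apply on their own terms. The natural sense of the Visit 1–3 sentence is that signs present at baseline are history. This largely answers the worst consequence. A reader might infer that a serious neurological event in screening would escape expedited reporting, and the documents do not support that. (Section 6.1.5 was not available for this check, and nothing is inferred from it.) The reply does not remove the conflict, because the paragraph goes on to set its own adverse-event rule without an exception.

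Other stronger readings are also tempting and do not hold:

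- *The examination is unanalysed or unused.* Recording new or changed findings as adverse events is mandatory, and Step 3 shows where they are summarized. Protocol 6.1.1.3 adds questionnaires and required laboratory tests for polyneuropathy.
- *All findings at Visits 1 to 3 are barred.* The sentence stands under Neurological Examination. Elsewhere in 5.3.1.1, laboratory abnormalities may be reported as adverse events.
- *An examination table would be less open to assessor bias than adverse-event reports.* Blinded raters are specified only for NMSS and PDSS-2, so the examination is also done in an open-label setting.
- *The missing table costs a calculable amount of power.* That would need event and abnormality rates that the documents do not give.

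**Conclusion.** The point holds in limited form and is minor. Protocol 5.3.1.1 contradicts 6.1.4 for serious and protocol-related neurological findings at Visits 1 to 3, and for the serious ones it also sits badly with the planned screening-period summary. Its start of recording for LCIG is later than that in 6.1.4. The neurological examination is the one measure of eight in SAP 4.6 without a dedicated summary of its results, which is narrower than having no analysis.

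No efficacy result, error rate or sample size is affected. The number of findings concerned cannot be estimated from the documents. The conclusion rests on a literal reading of 5.3.1.1; sites that treat Section 6.0 as overriding would record correctly. Whether examination components are captured as analysable data is not stated. The derived datasets in SAP 6.7 do not settle it, since they list no laboratory, vital-sign or ECG dataset either.

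**What to change.** 1. In Protocol 5.3.1.1, limit the Visit 1–3 sentence to findings that are neither serious nor protocol-related, and refer the rest to 6.1.4.
2. In the same paragraph, align the start of recording for the LCIG group with 6.1.4.
3. If examination results are captured as data, add to SAP section 10 a descriptive by-arm shift table or listing of the examination components, to each visit and to the worst value through Week 26. State one baseline, resolving Visit 1 against the last observation on or before randomization. SAP Table 2 has no row for the examination, so it would need visit windows.
4. If they are not captured, state in the SAP that the examination is analysed only through adverse events.

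The cost is two small edits to one protocol paragraph, plus either a little more programming or one sentence in the SAP. No extra visit or examination is needed.
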